16.4 Protection Against Study Risks

This section provides information on how adverse events and other risks to participants in the study will be mediated and specifies events that would preclude a participant from continuing with the intervention. This section also includes the informed consent procedures and measures to protect participants against risk during the study.

Informed Consent Process. This section explains the informed consent process and how it is used to protect participants.

- The consent process informs a volunteer about the study, indicates the participation is voluntary and he/she has the right to stop at any time. Risks are enumerated in the informed consent form and described orally during the consent process.
- Individuals will provide written or verbal informed consent prior to start of the baseline interview. Consent forms will only be used if they have a current IRB approval stamp. The informed consent process will be conducted in a manner to facilitate questions from potential study subjects. If a study team member is unable to answer a question, an investigator will be contacted. All questions from potential subjects should be answered prior to signature. The PI, a co-investigator, or an IRB-approved consent designee must be present when a subject signs the informed consent form. That

member of the study team must sign the informed consent form at the same time and in the presence of the subject. The consent form must be signed and dated by the subject and the consent designee. No subjects will be involved in research activities unless an investigator or a designated study staff has obtained documentation of legally effective informed consent of the subject. The collection of protected health information (PHI) and questionnaires are considered to be research activities requiring prior documentation of informed consent.

- Consent will only be sought under circumstances that provide the prospective subject sufficient opportunity to consider whether or not to participate and that minimize the possibility of coercion or undue influence. The information that is given to the subject or the representative shall be in language understandable to the subject. Potential study subjects will be given ample time to read and consider the consent form. All subjects will be reminded of the voluntary nature of study participation. Using the consent form to structure discussion, research personnel will explain the study, its potential benefits and risks, and alternatives, and document the consent process by signature of the subject and the person obtaining consent. During informed consent procedures, individuals will be told about possible risks and benefits of participation. This will include information that questions asked may cause them to feel uncomfortable or upset. They will be informed that: they may withdraw from an assessment at any time for any reason and receive full reimbursement for that assessment; and, they may withdraw from the research study at any time without negative consequences. Subjects are further informed that we will perform an immediate evaluation of their dangerousness towards self or others should safety concerns arise during assessments or intervention sessions. As well, they will be informed that we will contact their primary care physicians should concerns arise about medical or psychological risk. The staff will assess the participant's understanding of the study using an IRB-approved adapted version of the San Diego Brief Assessment of Capacity to Consent (UBACC), that we have implemented successfully in all of our studies with older adults. If a participant fails to answer all questions correctly, the staff will re-explain the study and then test the participant again. The consent will be an ongoing process during the study. Explanations of the study and verbal consent will be conducted at each data collection. Participants will be reminded that their participation is voluntary and that they can withdraw at any time for any reasons.

Protection Against Risks. This section describes measures to protect participants against study specific risks, as well as plans for notifying participants of trial results during and after the conclusion of the trial and providing the participants' health providers with the appropriate information from the trial, as needed, concerning individual participants. Study procedures, both assessments and interventions, pose minimal risk to participants. Below, we describe potential risks and study procedures to protect against these risks.

- In order to protect the confidentiality of subject information, we will take a number of precautions. These include training research interviewers in confidentiality procedures; entry and storage of data using coded identification labels; maintenance of project computers in secure locations with restricted access by enforced password protection; use of HIPAA compliant data management software (REDCAP). Back-ups of all study files will be made daily to allow for recovery of data due to disk failure. All data, including assessment measures, will be obtained with the written consent of the patient. Information pertaining to individual participants will be released with the patient's informed and written consent only, except in unusual cases where withholding the information might pose a serious risk or danger to the participant or others. All data will be identified by a uniquely

coded study number assigned to each participant. Access to the master list of study numbers will be restricted to the PI and the CRC. Confidentiality will be further maintained by the storage of "hard copy" data (if applicable) in locked files in a locked office. Access to computerized data is restricted and subject to review by the PI. Publications or presentations will report only cumulative data or descriptions certain to maintain participants' anonymity. All data collection involving human subjects will be HIPAA compliant. All data involving human subjects will be stripped of any identifiers; the data will be stored in a secure HIPAA compliant program called REDCAP, which manages protected health information in a HIPAA compliant manner. Audio recordings of semi-structured interviews will be transcribed and then destroyed to protect the security and confidentiality of identifiable information.

- In order to protect subjects' privacy, audio recordings of semi-structured interviews will only be made with subjects' written consent; subjects will be free to refuse to answer any questions they would prefer to not answer; interviews will be conducted in private settings. Participants will be given information in the consent form before joining the DLR intervention about the fact that the program is provided via Zoom and privacy limitations associated with videoconferencing software (which will be URMC HIPAA compliant).
- Risks associated with emotional distress or fatigue will be minimized by employment of research personnel with appropriate backgrounds and experience and work with psychological factors and elderly subjects. The baseline research interview will last approximately two hours in total. Given the length of time involved for this assessment, and concerns regarding subject health and well-being, subjects will be reminded that if they become fatigued, they may terminate the interview at any time, and that the interview can be conducted over multiple sessions as needed. Research personnel will further be trained to recognize potential signs of fatigue among elderly subjects, and to actively suggest alternative data collection strategies (including telephone-based and mail-in interviews), in order to reduce the possibility of overwhelming study subjects and to ensure completeness of data collection. These strategies have been employed effectively in the PI and Co-I's past research involving older adult populations.
 - During the course of assessment interviews, the CRC will monitor subjects' reactions for signs of distress or fatigue. If necessary, subjects may take breaks from the interview, or complete the interview over several sessions if fatigue becomes a concern.
 - If a subject's safety becomes a concern, the researcher will evaluate the subject's emotional state and safety. If the subject appears distressed, the CRC will briefly attempt to de-escalate the patient's distress. If these measures do not effectively reduce the patient's distress within 10-15 minutes and depending on the severity of the patient's distress, the CRC will call [name] (or the person covering for her), who will maintain a cell phone for this purpose. If neither is available, or if otherwise necessary, intervention will be provided by a clinician with Strong Behavioral Health's Older Adults Clinic, or by an on-call clinician in the University of Rochester Medical Center Community Mental Health Clinic (CMHC) or Psychiatric Emergency Department.
 - Given that we will be assessing depressive symptoms and subjects may report suicide ideation, the CRC's will be trained in the STAR Center's safety protocol for mental distress, suicide risk, and elder abuse, which involves items from the Columbia Suicide Severity Rating Scale and clinical interview. Subjects will be informed that study staff will perform an immediate evaluation of their dangerousness towards self or others should safety concerns

arise during assessments or treatment sessions. Subjects will also be informed that their confidentiality may be breached should concerns arise about their dangerousness to self or others. Finally, they will be informed that suspected child abuse will be reported, as mandated by law. Any subject who endorses death or suicidal ideation will be asked additional questions to assess his/her safety. Any endorsements of active suicidal ideation will involve notifying [name] for review of risk and protective factors and consideration of emergency psychiatric services. While it is expected (based on prior research) that only a small minority of subjects for the current study will report significant distress (and even fewer suicide ideation or elder abuse), CRC's will be trained in the study's safety protocol. A small minority of participants may experience elder abuse. In the case of suspected elder abuse, subjects will be given an immediate referral to the Elder Abuse Prevention Program provided in their region (this program is available nationally, typically through Area Agencies on Aging in all states). A phone call will be made to the primary care provider. Any suspected cases of elder abuse will be immediately reviewed with the PI before the CRC ends the assessment. Situations involving potential imminent dangerousness may involve the use of emergency services and law enforcement authorities. This safety protocol has been used successfully in STAR Center prior and on-going studies.

- The study PI ([name]) will provide regular supervision to research staff.

16.5 Data and Safety monitoring

This section describes who is responsible for data and safety monitoring, including type of information that will be reviewed and frequency of such reviews.

The purpose of the Data and Safety Monitoring Plan (DSMP) is to specify the procedures and rationales of the current study to ensure the safety of participants and the validity and integrity of the data. This specifies who will look at the data and review any adverse events, how often, and what they are authorized to do. The use of Data and Safety Monitoring Boards (DSMBs) may be indicated if studies have multiple clinical sites, are blinded (masked), and/or employ particularly high-risk interventions or vulnerable populations. This study on the other hand will be conducted utilizing a low risk intervention in a population of older adults residing independently in the community. Therefore, STAR Center Pilot Core leadership will be responsible for data and safety monitoring, including oversight of the DSMP and systematizing monitoring safety issues.

The Principal Investigator (PI) will be responsible for ensuring participants' safety on a daily basis. The STAR Center Pilot Core Director will act in an advisory capacity to the NIA Director and to evaluate the progress of the study, including periodic assessments of data quality and timeliness, participant recruitment, accrual and retention, participant risk versus benefit, performance of trial sites, and other factors that can affect study outcome. The committee will make recommendations to NIA's Director concerning the continuation, modification, or conclusion of the trial.

The STAR Center Pilot Core leadership will also provide a data processing, analysis and coordination function. This will be accomplished, in part, at the meetings of Pilot Core leadership with administrative reports by the PI that describe participants screened, enrolled, completed, and discontinued, as well as baseline characteristics of the study population. Given that this is a pilot study, further plans for data processing, analysis, and coordination are not warranted for this study. Interim analyses are not planned given the nature of this study.

16.5.1 Frequency of Data and Safety Monitoring

The STAR Center Pilot Core leadership will meet twice annually, either in-person or by teleconference call to review study progress, data quality, and participants safety. Safety reports are sent to the committee at least twice a year and will include a detailed analysis of study progress, data and safety issues.

16.5.2 Confidentiality

All materials, discussions and proceedings of the data safety monitoring meetings are completely confidential. Members and other participants in such meetings are expected to maintain confidentiality.

16. DATA ANALYSIS PLAN

16.1 Sample Size Considerations: In order to assess feasibility, using a reference of 0.5 for consent and adherence rate, 40 dyads would achieve 83% power using a one-tailed test at significance of 0.05. The quantitative data will be used to guide sample size calculations for a future randomized pilot. Therefore, a sample of 40 patient/caregiver dyads will support the assessment of feasibility of the telehealth DLR with older patients and caregivers and allow for thematic saturation through qualitative semi-structured interviews.

16.2. Analysis of Aims:

16.2.1 Primary aim: To evaluate the feasibility of enrolling and delivering the telehealth DLR intervention, we will calculate proportion of: 1) approached patient/caregiver dyads who enrolled (70%); 2) enrolled dyads who completed all 8 DLR sessions (70%); and 3) general acceptability of the DLR intervention by patients and caregivers. General acceptability will be examined through coding of transcribed semi-structured interviews from the 40 dyads (separate interviews for patients and caregivers; 40 patient interviews and 40 caregiver interviews). A sub-group analysis will examine any differences between older patients with only advanced cancer and their caregivers and older patients with both advanced cancer and MCI and their caregivers in enrollment, adherence, and acceptability.

16.2.2 Secondary and Exploratory Aims: To examine the pre-post change in caregiver psychological distress, we will utilize a regression analysis that will include the pre-measurement of caregiver distress as a covariate. We will also include gender and income as covariates in this model. A regression analysis will also be used to examine changes in the exploratory measures using the same covariates. A sub-group analysis will compare the difference in changes from pre to post intervention between dyads that include older patients with only advanced cancer and dyads with older patients with both advanced cancer and MCI.

16.2.3 Mixed Methods Aim:

Qualitative Data Analysis: Semi-structured interviews will be audio-recorded and transcribed into MAXQDA software for coding and analysis. Abductive analysis will be used to code transcribed interviews and extract themes. Two independent coders will code the data until thematic saturation is achieved. Coding will be compared and discrepancies resolved through an iterative process and achieving consensus. Semi-structured interviews will gather information about the acceptability of the intervention, perceptions of the dyadic approach to the interventions, and evaluate patient and caregiver perceptions of communal coping. A sub-group coding analysis will be performed to examine any differences in responses between older patients with only advanced cancer and their caregivers and older patients with both advanced cancer and MCI and their caregivers.

Integration: Qualitative and quantitative data, including baseline and follow up measures and

transcribed semi-structured interviews, will be integrated to develop a more complete understanding of the feasibility of a telehealth DLR intervention in this unique population and to gain understanding of the patient and caregiver experiences and gather thick descriptions about barriers and facilitators for the intervention. The qualitative data can provide explanatory data for any changes in the quantitative measures from pre to post intervention for both patients and caregivers.

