1. PURPOSE OF STUDY

The purpose of this study is to test the feasibility of a telehealth Dyadic Life Review (DLR), adapted from individual Life Review Therapy, with caregivers of older adults with advanced cancer, including those with Mild Cognitive Impairment (MCI). The study will enroll dyads of caregivers and older patients with advanced cancer and dyads of caregivers and patients with advanced cancer and Mild Cognitive Impairment (MCI). Life Review Therapy has only been delivered individually and there are no dyadic mental health interventions designed to target the mechanism of communal coping and reduce distress and emotional health outcomes in both older patients with advanced cancer and their caregivers. This innovative pilot study will gather data to test the feasibility of adapting Life Review Therapy to be delivered as a dyadic life review (DLR) and examine pre-post intervention changes in caregiver psychological distress.

1.1. Objective and Specific Aims (40 patient/caregiver dyads):

Objective: The research team will adapt and refine a dyadic life review intervention for older patients with advanced cancer, older patients with advanced cancer and MCI, and their caregivers. A mixed methods (i.e., integration of qualitative and quantitative data) approach will be used to gain understanding of the usability and feasibility of a telehealth DLR intervention with older adults with advanced cancer and their caregivers and examine effects on distress and emotional health in both the patient and caregiver.

1.2 Primary Aim:

1.2.1 To evaluate the feasibility of the dyadic life review intervention in older patients advanced cancer, with or without MCI, and their caregivers by determining consent rate, intervention adherence rate, and patient/caregiver acceptability. Hypothesis: We will achieve a dyad consent rate of 70%, dyad intervention adherence rate of 70%, and the intervention will be generally acceptable by dyads (determined from semi-structured interviews).

1.3 Secondary Aims:

1.3.1 To examine the pre-post change in the primary outcome of caregiver self-reported psychological distress, and secondary outcomes of caregiver loneliness, relationship satisfaction, and mental health outcomes, and changes in the associations between patient and caregiver distress.

1.4 Mixed Method Aim:

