4. STUDY DESIGN

Forty dyads will be enrolled in a single-arm mixed methods intervention trial in order to evaluate the feasibility of enrolling older patients with advanced cancer, older patients with advanced cancer and MCI, and their caregivers. This single-arm feasibility study will allow the PI and the team to develop and examine the feasibility of a telehealth-based DLR intervention that has not previously been adapted or tested in these populations. A pre-post test design will be used to measure effects of the DLR intervention on the primary outcome of psychological distress in caregivers. Patients and caregivers will undergo separate semi-structured interviews.

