8. STUDY PROCEDURES

8.1 Measures:

Patient measures will include demographics, cognitive, psychological, and functional independence measures.

Demographics: Patient and caregiver demographics will be collected, including age, gender, race, ethnicity, marital status, education and socio-economic status will be captured. Cancer and treatment variables, comorbidities, and medications list will be collected from the medical record by study staff.

Questionnaires: Psychosocial, survey-style questionnaire assessments will be conducted at baseline and post-intervention, will take less than 1 hour, will consist primarily of quantitative (closed-ended) questions, and will employ the REDCap online survey system, licensed to the University of Rochester, for patients and caregivers to complete on their own. The REDCap questionnaires will be coded by a member of the study team who has experience coding and creating questionnaires and with the methodology of REDCap questionnaire entry.

Patient Measures	Target Aim	Information
UCLA Loneliness Scale, short-form	Secondary Aim: support recruitment to reach maximum variation of caregiver loneliness scores	Score of 6 or greater indicates loneliness
Unidimensional Relationship Closeness Scale	Secondary Aim: relationship domain	Quality of relationship with care-receiver: assesses quality of relationship between participant and family member and has demonstrated valid

		scores across several relationship types, including spouses and other family members
PROMIS29	Secondary Aim: mental health and physical health domains	Assesses for seven domains of depression, anxiety, physical function, pain interference, fatigue, sleep disturbance, and ability to participate in social roles.
Perceived Stress Scale	Secondary Aim: mental health domain	Measure the degree to which situations are appraised as stressful
Geriatric Depression Scale (GDS)	Secondary Aim: mental health domain	Identify clinical threshold of depression in older adults
Distress Thermometer and Problem List	Secondary Aim: primary outcome	10-point self-report measure to capture distress and identify a list of sources of that distress
Dyadic Adjustment Scale-7 (DAS-7)	Secondary Aim: relationship domain	7-item measure to assess relationship quality
Dyadic Support Questionnaire (DSQ)	Secondary Aim: relationship domain	18-item measure to assess individual's perceptions of received and provided support.

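### Section 16.2.2 names no parameter that estimates mean pre-post change in caregiver distress in this single-arm trial, and gives no analysis for the patient-caregiver distress association in Aim 1.3.1

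*Combined protocol and SAP*

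**What the plan says.** Section 4 sets the design: "Forty dyads will be enrolled in a single-arm mixed methods intervention trial". It gives the purpose of the two measurements: "A pre-post test design will be used to measure effects of the DLR intervention on the primary outcome of psychological distress in caregivers".

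Aim 1.3.1 asks for the pre-post change in caregiver distress. It then lists "secondary outcomes of caregiver loneliness, relationship satisfaction, and mental health outcomes, and changes in the associations between patient and caregiver distress".

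The analysis is in Section 16.2.2 of the Data Analysis Plan: "To examine the pre-post change in caregiver psychological distress, we will utilize a regression analysis that will include the pre-measurement of caregiver distress". Two further covariates follow: "We will also include gender and income as covariates in this model". For other measures: "A regression analysis will also be used to examine changes in the exploratory measures using the same covariates". The last sentence of 16.2.2 compares changes between dyads with and without mild cognitive impairment (MCI).

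Neither 16.2.2 nor 16.2.3 says whether the dependent variable is the post-intervention score (Time Point 2, TP2) or the change from baseline (TP1). Neither says whether covariates are centred or which parameter answers the aim. Neither contains an analysis of the association between patient and caregiver distress.

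**The concern.** Adjusting for baseline works well when a group term carries the treatment effect. This trial has no group term. The coefficients that 16.2.2 names describe which caregivers end higher or lower. They do not say whether caregivers as a whole moved. The aim asks the second question and the model as written answers the first.

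At stake is the reported result for the main outcome of the secondary aim. Section 16.1 wants the quantitative data to guide sample size for a later randomised pilot, and Section 16.2.3 uses the interviews to explain pre-post changes. Both need the change to be estimated, and the plan names neither the mean change nor its SD. If the choice is left open, it will be made after the data are seen.

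**Working it through.** **Inputs.** From the documents: 40 dyads in one arm (Section 4); one baseline and one follow-up assessment (Section 8.1); covariates of baseline distress, gender and income (16.2.2). The documents give no mean, SD or correlation for the Distress Thermometer, so those below are assumptions. The low case of 28 complete pairs is 0.70 × 40. It borrows the target for completing all eight sessions, and the documents do not equate that with having TP2 data.

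**The plan's own figure.** The only power figure is 83% in 16.1. It reproduces: Φ{[(0.7 − 0.5)√40 − 1.645√0.25] / √0.21} = Φ(0.965) = 0.833. It concerns consent and adherence rates. Nothing comparable is given for distress.

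**Step 1: the slopes.** Write TP2 = a + b·TP1 + g·gender + h·income + error. Add a constant c to every TP2 score. Least squares gives a + c for the intercept and leaves b, g, h, the residuals, the slope p-values and R-squared as they were. One simulated data set of 40:

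| Added to every TP2 score | Mean change | Slopes (TP1, gender, income) | R-squared | Intercept |
|---|---|---|---|---|
| −2 | −2.34 | 0.631, −0.695, 0.061 | 0.367 | −0.03 |
| 0 | −0.34 | 0.631, −0.695, 0.061 | 0.367 | 1.97 |
| +2 | +1.66 | 0.631, −0.695, 0.061 | 0.367 | 3.97 |

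This step is algebra and needs no assumed values.

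**Step 2: the intercept under default coding.** Let m be the baseline mean and D the true mean change, with gender and income unrelated to distress. With TP1 uncentred, intercept = (m + D) − b·m = m(1 − b) + D. With the change score as outcome the slope is b − 1, and D − (b − 1)m is the same number. Under no change (D = 0):

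| m | b = 0.4 | 0.5 | 0.6 | 0.7 |
|---|---|---|---|---|
| 3 | 1.8 | 1.5 | 1.2 | 0.9 |
| 4 | 2.4 | 2.0 | 1.6 | 1.2 |
| 5 | 3.0 | 2.5 | 2.0 | 1.5 |

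For a true 1-point fall, subtract 1 from each cell. A simulation (n = 40, m = 5, SD 2.5, pre-post correlation 0.5, 4000 runs) agrees. The intercept averaged 2.50 with no change and 1.51 with a 1-point fall. The paired mean averaged −0.005 and −1.001.

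**Step 3: the favourable reading.** With change as outcome and all covariates mean-centred, the intercept equals the mean change exactly. Its ordinary standard error treats the sample baseline mean as fixed and is too small. At SD 2.5 and correlation 0.5, the SD of change is 2.5√(2 × 0.5) = 2.5 and the residual SD is 2.5√(1 − 0.25) = 2.165. The 95% half-widths are 2.023 × 2.5/√40 = 0.80 (paired) and 2.028 × 2.165/√40 = 0.69 (regression). In the same simulation the regression test rejected a true null in 8.4% of runs at nominal 5%, against 4.6% for the paired t-test.

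**Step 4: what the paired estimate would deliver.** Half-width = t(0.975, n − 1) × SD of change / √n.

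| n | SD 2 | SD 2.5 | SD 3 |
|---|---|---|---|
| 40 | 0.64 | 0.80 | 0.96 |
| 28 | 0.78 | 0.97 | 1.16 |

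**Step 5: the association.** A patient-caregiver correlation of 0.3 at one time point has a 95% CI of tanh(0.310 ± 1.96/√37), about −0.01 to 0.56, with 40 dyads. For the TP2 minus TP1 difference in correlations, simulation (dyad correlation 0.2 to 0.4, within-person correlation 0.5 to 0.7) gives a 95% half-width of 0.27 to 0.37 with 40 dyads and 0.32 to 0.45 with 28. It can be described but hardly tested.

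**The case against.** The strongest reply is that silence is not a wrong model. Section 16.2.2 says only that a regression will be used. Change as outcome with centred covariates, or an adjusted mean at average covariate values, would give the mean change, and nothing rules these out. That stands: a reader might infer that the model cannot yield mean change at all, and the documents do not support so strong a claim. What remains is that the plan states none of the choices that would make it do so, and the centred version still has too narrow an interval (step 3).

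Second, the MCI comparison in 16.2.2 requires a change in each group, and Aim 1.4.1 and Section 16.2.3 speak of changes to be explained. So someone will compute changes. But the MCI comparison targets a difference: if both groups fell by one point it would show zero. The other two assume an estimate without defining it.

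Third, a reader might infer from step 2 that the trial would report distress moving the wrong way. The documents do not say that anyone will present the intercept as the change, and with TP2 as outcome it is a predicted score. How often it would mislead also depends heavily on the assumed mean and correlation. Step 2 shows what the intercept is not; it does not predict an error.

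Fourth, a reader might infer that patient change is an unmet aim, since Objective 1.1 intends to "examine effects on distress and emotional health in both the patient and caregiver". Aim 1.3.1 and Section 4 tie pre-post change to caregivers, Section 16.2.3 expects patient changes as input, and Section 14 allows post hoc use of all data. That is a matter of wording and is not pressed here.

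Finally, this is a secondary aim of a feasibility pilot and the paired data will exist. That limits the consequence but does not supply the missing analysis.

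**Conclusion.** The point holds as a gap in specification that matters for the aim. The covariate slopes cannot show mean change under any coding, and with uncentred coding the intercept does not show it either. The plan names no other estimate. The missing analysis of the patient-caregiver association holds without qualification.

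If the phrase exploratory measures is read broadly, as the heading of 16.2.2 invites, the other caregiver outcomes in Aim 1.3.1 inherit the same gap. If it is read narrowly, they have no model.

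The slope result rests on no assumption. The sizes are illustrative: an intercept 0.9 to 3.0 points above the true change for a baseline mean of 3 to 5 and slope of 0.4 to 0.7, and a paired half-width of 0.64 to 0.96 points with 40 caregivers for an SD of change of 2 to 3. A correct estimate remains available from the planned data, and the primary feasibility conclusion does not depend on any of this.

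**What to change.** Amend Section 16.2.2 as follows.

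- **Mean change.** State that the result for Aim 1.3.1 is the paired mean change (TP2 minus TP1) in the caregiver Distress Thermometer, with the SD of change and a paired-t 95% CI. Give the same summary for the caregiver loneliness, relationship satisfaction and mental health outcomes.
- **Regression.** Keep it only to describe which caregivers change, with change as outcome and TP1 distress, gender and income mean-centred.
- **Association.** In dyads with both time points, report the patient-caregiver Distress Thermometer correlation at TP1 and at TP2. Report their difference with a bootstrap 95% CI that resamples dyads. Label it descriptive.

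The cost is a few sentences, with no new measure, visit or participant. Two limits remain and should be stated. A one-arm change cannot separate the intervention from time or regression to the mean. Summarising more scales also gives more chance findings, so results beyond the caregiver Distress Thermometer should stay descriptive.
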